8. RISKS AND BENEFITS

List all potential physical, psychological, social, financial or legal risks to subjects (risks listed here should be included on the consent form).

There are no known risks associated with obtaining consent, height, weight, a resting ECG, resting blood pressure, urine analysis or using ultrasound to measure blood flow.

Hydration Protocol

There are some risks when old participants are asked to limit water intake during the water restriction protocol. During the water restriction protocol participants may develop a dry mouth, develop thirst, become tired, develop a headache, develop constipation, or become dizzy or light headed. This protocol is designed to induce mild dehydration and we have identified strategies and remedies to prevent moderate to severe dehydration. First, participants will not be exercising prior to the water restriction therefore activity will not contribute to the mild dehydration. Second, participants will be told to swish water in their mouth and spit it out as needed to reduce thirst. If participants do begin to feel the more severe forms of dehydration (severe headache, extreme thirst, very dry mouth) they will be instructed to consume 8oz of water and if symptoms are not resolved within 30 minutes, participants will be instructed to consume another 8oz of water. We anticipate quick resolution of any dehydration related symptoms after the consumption of 8oz of water, however if symptoms are present after 30 minutes they will be instructed to contact the investigators and if necessary seek medical attention.

The technique of mild dehydration through short-term water restriction is an accepted and safe technique. Included is a list of five published papers where this technique has been used (1-5):

1. Armstrong, L. E., et al. "Thermal and Circulatory Responses during Exercise: Effects of Hypohydration, Dehydration, and Water Intake." *Journal of applied physiology* (Bethesda, Md.: 1985) 82.6 (1997): 2028-35. Print.
2. Charkoudian, N., et al. "Interactions of Plasma Osmolality with Arterial and Central Venous Pressures in Control of Sympathetic Activity and Heart Rate in Humans." *American journal of physiology. Heart and circulatory physiology* 289.6 (2005): H2456-60. Print.
3. Judelson, Daniel A., et al. "Effect of Hydration State on Strength, Power, and Resistance Exercise Performance." *Medicine and science in sports and exercise* 39.10 (2007): 1817. Print.

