In order to minimize risks, the heart rate and blood pressure will be monitored throughout testing. Should we see excessive blood pressure increases or heart rate irregularities, we will terminate the testing visit.

Hydration Protocol

Following the water restriction protocol data collection visit, participants will be told to consume water. If any symptoms of mild dehydration are present, we anticipate quick resolution after the consumption of 8-16oz of water. In the event that someone would require medical treatment, they will be referred to the Nurse Managed Primary Care Center.

As stated, there are potential risks associated with short term water restriction. In order to mitigate these risks and discomfort, they will be instructed to swish water in their mouth, refrain from strenuous exercise, and avoid hot environments for extended periods of time. If participants do begin to feel the more severe forms of dehydration (severe headache, extreme thirst, very dry mouth) they will be asked to consume 8oz of water and if symptoms are not resolved within 30 minutes, participants will be instructed to consume another 8oz of water. If symptoms persist, participants will be instructed to contact the investigators and if necessary seek medical attention.

Old adults may be more susceptible to dehydration related symptoms. We will monitor them closely during the dehydration protocol and instruct them to consume water if they begin to feel more severe symptoms of dehydration (listed above).

Catheter Insertion & Blood Draw

Standard safety precautions will be taken when drawing blood samples and placing IV catheters. To minimize the risk of infection associated with blood collection, only sterile, single use catheters will be used. To minimize the risk of bruising, proper blood collection technique will be utilized.

Tests of Sympathetic Reactivity

Participants will be re-assured that at any time during the protocol, if they feel too uncomfortable to continue than we will stop testing. Blood pressure will be continuously monitored during exercise. If there is an excessive increase in blood pressure, defined as systolic blood pressure above 220 mmHg or diastolic blood pressure above 110 mmHg, exercise will be terminated.

Isometric Handgrip Exercise and Post Exercise Ischemia Trial

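### Dizziness is a listed risk of water restriction but is missing from the symptoms that tell an older participant to drink rescue water

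*Protocol*

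**What the plan says.** Only old adults (55-75 years) undergo water restriction. Protocol section 8, under Hydration Protocol, lists six possible effects: dry mouth, thirst, tiredness, headache, and the last two, "develop constipation, or become dizzy or light headed".

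The same paragraph then gives the rescue instruction, for "more severe forms of dehydration (severe headache, extreme thirst, very dry mouth) they will be instructed to consume 8oz of water". A second 8 oz follows if symptoms have not cleared in 30 minutes. It continues: "We anticipate quick resolution of any dehydration related symptoms after the consumption of 8oz of water", and symptoms still present after 30 minutes lead to contact with the investigators and medical attention if needed.

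The Hydration Protocol text under the steps to minimize risks, also in section 8, repeats the rule with the same three symptoms: "more severe forms of dehydration (severe headache, extreme thirst, very dry mouth) they will be asked to consume 8oz of water". It ends the sequence with "If symptoms persist, participants will be instructed to contact the investigators". It then says "Old adults may be more susceptible to dehydration related symptoms", promises close monitoring of this group, and undertakes to "instruct them to consume water if they begin to feel more severe symptoms of dehydration (listed above".

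**The concern.** During restriction a participant's default is to stay within a fluid quota. In the section 6 table (70 kg example) the quota falls to 40 oz on day 2 and 24 oz on day 3, with no fluids on the visit morning. The trigger list is the stated exception to that quota, so a symptom left off it gives a compliant participant no stated reason to drink.

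Among the listed effects without a trigger, dizziness deserves separate attention. It may signal falling blood pressure, and a fall or faint at home is a real hazard at this age. The protocol itself supplies the context: section 6 uses dizziness as an example of a symptom that keeps an old adult out at screening, and section 8 rates the study as more than minimal risk partly because of water restriction in old adults. What is at stake is participant safety while away from the laboratory. No estimate, test or sample size depends on it.

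**Working it through.** The protocol gives no figure to reproduce here. The check has two parts: a comparison of the texts, and a costing of the remedy.

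**Listed risks against triggers (both in section 8)**

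| Listed risk | Trigger in risk text | Trigger in risk-minimization text |
|---|---|---|
| Dry mouth | yes, if very dry | yes, if very dry |
| Thirst | yes, if extreme | yes, if extreme |
| Headache | yes, if severe | yes, if severe |
| Tiredness | no | no |
| Constipation | no | no |
| Dizziness or light-headedness | no | no |

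Three of six listed risks have a severe form that triggers rescue water. Dizziness is in 0 of 2 lists. The parenthesis is not introduced as a set of examples, and the old-adult safeguard treats it as a defined list by pointing back to it.

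**Whether other provisions supply the instruction**

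- The sentence on quick resolution covers any dehydration symptom, but it describes what is expected once 8 oz has been drunk. The only instruction to drink that 8 oz during restriction is the three-symptom one.
- Contact if symptoms persist is the last step of the same sequence, so it is reached through the same trigger.
- Exclusion for adverse side effects of restriction (section 7) is an investigator's decision, not advice to a participant at home.
- Close monitoring of old adults is promised without a method or contact schedule, and the drinking instruction attached to it uses the same list.
- "In the event that someone would require medical treatment, they will be referred to the Nurse Managed Primary Care Center" stands in the paragraph about the period after the data collection visit and applies to someone who needs treatment.

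**Cost of adding a trigger**

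Inputs are from the section 6 hydration table, 70 kg example:

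- Normal hydration: 54 + 54 + 54 + 8 = 170 oz.
- Water restriction: 54 + 40 + 24 + 0 = 118 oz.
- Planned difference: 170 - 118 = 52 oz. Of this, day 2 gives 54 - 40 = 14 oz, day 3 gives 54 - 24 = 30 oz and the visit morning gives 8 oz.
- Late difference (day 3 and visit morning): 30 + 8 = 38 oz.

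Share of one user's difference removed by rescue water, taking it as additional to the quota:

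- Whole period: 8/52 = 15.4% to 16/52 = 30.8%.
- Late period only: 8/38 = 21.1% to 16/38 = 42.1%.

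Mean loss of planned separation = proportion using it because of the new trigger x per-user share. The protocol gives no rate, so 5% and 20% are assumptions:

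- At 5%: 0.05 x 15.4% = 0.8% to 0.05 x 30.8% = 1.5% of 52 oz; 0.05 x 21.1% = 1.1% to 0.05 x 42.1% = 2.1% of 38 oz.
- At 20%: 0.20 x 15.4% = 3.1% to 0.20 x 30.8% = 6.2% of 52 oz; 0.20 x 21.1% = 4.2% to 0.20 x 42.1% = 8.4% of 38 oz.

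**The case against.** The strongest reply is that nothing here is inconsistent. A study meant to induce mild dehydration should expect mild symptoms and keep rescue water for worse ones; tiredness and constipation have no trigger either. That stands as far as it goes: the severity threshold is a legitimate design choice, and listing a risk without making it a trigger is no contradiction. It does not explain why no degree of dizziness, however marked, qualifies.

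A reader might infer that a dizzy participant is left unprotected. The document does not support that. Restriction is not abstention until the visit morning, old adults are to be monitored closely, participants are told to avoid strenuous exercise and prolonged heat, and a person with adverse side effects can be excluded. The gap is narrower: none of these is an instruction to drink.

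A reader might also infer that participants are in fact never told what to do when dizzy. That cannot be established either. The water restriction packet (listed in section 15) and the old-adult consent form are not shown and may already cover it.

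Finally, a reader might conclude that any light-headedness should trigger water. An ungraded term would sit badly beside severe, extreme and very, and would release water for brief symptoms that the study expects. The screening criterion does not support it: there dizziness is an example of a sign of disease, and it does not grade a transient effect of planned restriction.

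**Conclusion.** The point holds as a gap in protocol wording. The rescue rule is written out twice, is reused for the group described as more susceptible, and omits a symptom that the same section lists as a risk. The other provisions give general protection but do not tell a participant at home to drink for dizziness.

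Its weight is low. The conclusion rests on reading the three symptoms as a closed list and concerns the protocol text only. The frequency of dizziness under restriction is not given, so the size of the harm cannot be estimated. The remedy's cost is material for an individual user but small on average if use is uncommon. It is worth making because it is cheap.

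**What to change.** In both Hydration Protocol texts of section 8, add a graded term to the trigger list, for example: *persistent or marked dizziness or light-headedness, or any fainting or near-fainting*. Attach the existing action unchanged: 8 oz of water, a second 8 oz if unresolved at 30 minutes, then contact with the investigators if symptoms persist, and medical attention if necessary. The old-adult safeguard then covers dizziness through its back-reference and needs no edit of its own. Check that the water restriction packet carries the same list.

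The work is a wording change in two places and one document check. The price is some additional rescue water and calls, and the modest loss of planned separation costed above.

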In order to minimize risks, the heart rate and blood pressure will be monitored throughout testing. Should we see excessive blood pressure increases or heart rate irregularities, we will terminate the testing visit.

Hydration Protocol

Following the water restriction protocol data collection visit, participants will be told to consume water. If any symptoms of mild dehydration are present, we anticipate quick resolution after the consumption of 8-16oz of water. In the event that someone would require medical treatment, they will be referred to the Nurse Managed Primary Care Center.

As stated, there are potential risks associated with short term water restriction. In order to mitigate these risks and discomfort, they will be instructed to swish water in their mouth, refrain from strenuous exercise, and avoid hot environments for extended periods of time. If participants do begin to feel the more severe forms of dehydration (severe headache, extreme thirst, very dry mouth) they will be asked to consume 8oz of water and if symptoms are not resolved within 30 minutes, participants will be instructed to consume another 8oz of water. If symptoms persist, participants will be instructed to contact the investigators and if necessary seek medical attention.

Old adults may be more susceptible to dehydration related symptoms. We will monitor them closely during the dehydration protocol and instruct them to consume water if they begin to feel more severe symptoms of dehydration (listed above).

Catheter Insertion & Blood Draw

Standard safety precautions will be taken when drawing blood samples and placing IV catheters. To minimize the risk of infection associated with blood collection, only sterile, single use catheters will be used. To minimize the risk of bruising, proper blood collection technique will be utilized.

Tests of Sympathetic Reactivity

Participants will be re-assured that at any time during the protocol, if they feel too uncomfortable to continue than we will stop testing. Blood pressure will be continuously monitored during exercise. If there is an excessive increase in blood pressure, defined as systolic blood pressure above 220 mmHg or diastolic blood pressure above 110 mmHg, exercise will be terminated.

Isometric Handgrip Exercise and Post Exercise Ischemia Trial

Tightness in the forearm will occur with the inflation of the cuff during post exercise ischemia. The release of the cuff and influx of blood back into the arm may produce a “pins and needles” or “flushed” sensation. Additional risks associated with this procedure may include: soreness and stiffness of the forearm after the procedure, damage to the veins, thrombosis, and lightheadedness. If cuff inflation becomes too uncomfortable for the participant, the cuff will be immediately released.

Hand in Cold Water Test

During the test, we will be monitoring the participant’s blood pressure and heart rate. Should we see excessive increases in blood pressures or abnormal arrhythmias we will stop the test and begin recovery.

Microneurography

The time limit of one hour for finding a usable recording site will be strictly enforced. In the event a participant experiences adverse symptoms during the procedure, the protocol will be stopped. Participants will be warned about the risks of any discomfort. Participants will also be told that they can discontinue the study at any time. Participants will be directed to monitor for signs of infection (redness, soreness, heat and/or discharge) for 3-5 days post-study at the catheter and microelectrode placement sites. Should signs of infection occur, participants will be asked to contact the study investigators.

Describe any potential direct benefits to participants.

None

Describe any potential future benefits to this class of participants, others, or society.

The current proposal will give insight into the effect of decreased water intake on sympathetic nerve activity (commonly referred to as the fight or flight response) and blood pressure responses in older adults. We will increase the understanding of how the body maintains cardiovascular homeostasis by managing blood electrolyte and body water levels under various hydration states. These tests will provide specific insight into whether hydration status directly impacts the sympathetic nervous system and reflexes related to the sympathetic nervous system. Additionally, this investigation will provide novel information on cardiovascular regulation during mild dehydration in aging.

If there is a Data Monitoring Committee (DMC) in place for this project, please describe when and how often it meets.

No

9. COMPENSATION

Will participants be compensated for participation?

Yes

If so, please include details.

Old adults:

\$150 for full completion of the research protocol (6 visits).

\$130 if they complete one of the two three-hour experimental visits, and not physical activity monitoring.

Young adults:

\$85 for full completion of the research protocol (4 visits).

\$65 if they complete one of the one three-hour experimental visits, and not physical activity monitoring.

10. DATA

Will subjects be anonymous to the researcher?

No

If subjects are identifiable, will their identities be kept confidential? (If yes, please specify how)

Individual identity will be known only to the investigators. Participants will not be individually identified, except by participant number. All identifying information will be separated into a different locked filing cabinet. A participant number provided to each individual participant will be associated with all data collected. A participant key linking participant ID and name will be kept on a password-protected computer managed by the Principal Investigator.

How will data be stored and kept secure (specify data storage plans for both paper and electronic files. For guidance see <http://www.udel.edu/research/preparing/datastorage.html>)

The paper files are stored in a locked cabinet. Digital files containing only de-identified data are stored on a password-protected computer or password protected encrypted file. While the results of the research may be published, participants' names and identities will not be revealed.

How long will data be stored?

All data will be stored in a locked cabinet or password protected computer indefinitely.

Will data be destroyed? YES NO (if yes, please specify how the data will be destroyed)

We propose keeping the data indefinitely, but destroying the document linking the participant names/identifying information to the data, 5 years after study closeout.

Will the data be shared with anyone outside of the research team? YES NO (if yes, please list the person(s), organization(s) and/or institution(s) and specify plans for secure data transfer)

How will data be analyzed and reported?

Coded data will be analyzed using several statistical software packages. The results and interpretation will be published in peer-reviewed journals.

11. CONFIDENTIALITY

Will participants be audiotaped, photographed or videotaped during this study?

No

How will subject identity be protected?

Participants will not be individually identified, except by a participant number known only to the investigators.

Is there a Certificate of Confidentiality in place for this project? (If so, please provide a copy).

No

12. CONFLICT OF INTEREST

(For information on disclosure reporting see:

<http://www.udel.edu/research/preparing/conflict.html>)

Do you have a current conflict of interest disclosure form on file through UD Web forms?

No

Does this project involve a potential conflict of interest*?

No

* As defined in the [University of Delaware's Policies and Procedures](#), a potential conflict of interest (COI) occurs when there is a divergence between an individual's private interests and his or her professional obligations, such that an independent observer might reasonably question whether the individual's professional judgment, commitment, actions, or decisions could be influenced by considerations of personal gain, financial or otherwise.

If yes, please describe the nature of the interest

13. CONSENT and ASSENT

Consent forms will be used and are attached for review (see Consent Template under Forms and Templates in IRBNet)

Additionally, child assent forms will be used and are attached.

Waiver of Documentation of Consent (attach a consent script/information sheet with the signature block removed).

Waiver of Consent (Justify request for waiver)

14. Other IRB Approval

Has this protocol been submitted to any other IRBs?

No

If so, please list along with protocol title, number, and expiration date.

15. Supporting Documentation

Please list all additional documents uploaded to IRBNet in support of this application.

1. **Protocol (TC and clean)**
2. **Young adult consent (TC and clean)**
3. **Old adult consent (TC and clean)**
4. **Young adult advertisement with tabs (new)**
5. **Young adult advertisement without tabs (new)**
6. **Old adult advertisement with tabs (TC and clean)**
7. **Old adult advertisement without tabs (TC and clean)**
8. **Recruitment scripts (TC and clean)**
9. **Normal hydration protocol packet (clean)**
10. **Water restriction protocol packet (clean)**
11. **Medical history form (clean)**
12. **PAR-Q (clean)**
